## 5. OBJECTIVES

The aim of this pilot randomized controlled trial (RCT) is to gather preliminary clinical, health economic and safety data on the use of ALNB in the treatment of chronic wounds, for post-market surveillance and to assist with planning future research concerned with the efficacy and cost-effectiveness of ALNB.

## **5.1 PRIMARY**

The primary objective is to estimate the effect of treatment with ALNB on HRQoL in subjects with chronic ulcers, measured using the CWIS-PSDL (Physical Symptoms of Daily Living) scale, compared to subjects receiving SC alone, over a six-week treatment period.

## **5.2 KEY SECONDARY**

To estimate the effects of treatment with ALNB, when compared with SC alone, on HRQoL measured by the CWIS-PSDL scale at three and twelve weeks, and CWIS well-being (WB), social life (SL); global quality of life (GQ); and satisfaction with quality of life scales (SQ); at three, six, and twelve weeks.

## **5.3 SECONDARY**

Secondary objectives of this study are:

- Ulcer progression (including undermining, necrotic tissue type and amount, exudate type and amount, skin color surrounding the wound, granulation tissue, epithelialization, condition of peri-wound, ulcer dimensions and healing status) at three, six, and twelve weeks
- Healthcare resource use related to the reference ulcer (including number and cost of dressings used, consultations and time used by healthcare professionals (HCP), time in hospital, number and cost of additional treatments, procedures, and investigations) over twelve weeks

## **5.4 EXPLORATORY**

The exploratory objective of this study is to compare differences between ALNB and SC in dressing performance (including wear time, leakage, odor control, and absorption under compression) and usability (including comfort and ease of application/removal together with associated pain) at three, six, and twelve weeks

## 5.5 SAFETY

Safety data will be gathered throughout the twelve weeks of the study including:

- Adverse events
- Device deficiencies

## 5.6 CLAIMS

The study is a pilot RCT, which will enroll a small sample of subjects with a range of chronic, moderate to highly exuding ulcer types: LU (arterial/mixed etiology leg ulcers or venous leg ulcers requiring compression therapy), PU, and non-ischemic DFU. Data generated from this study are unlikely to be sufficient to demonstrate any statistically significant difference in observed clinical outcomes between devices. Nevertheless, this study will generate the first comparative clinical, economic, and safety data for use of ALNB in subjects, and will extend current evidence for the ALLEVYN LIFE product range.

This pilot RCT may provide preliminary data as supporting evidence for the existing product claims.

## 6. STUDY PRODUCT

### 6.1 IDENTIFICATION

#### 6.1.1 Test Product: ALLEVYN LIFE Non-Bordered

*Intended use*

ALNB is intended for use in wound management by secondary intention on shallow, granulating wounds, chronic and acute exudative wounds, full- and partial-thickness wounds including:

- Pressure ulcers
- Leg ulcers
- Diabetic foot ulcers
- Surgical wounds
- First- and second-degree burns

- Skin graft donor sites
- Skin tears
- Fungating wounds

The present study aims to evaluate the use of ALNB for adult ( $\geq 18$  years of age) subjects with moderate to highly exuding chronic ulcers that, in the opinion of the Investigator, would benefit from a protective dressing but do not require a topical antimicrobial treatment, limited to:

- Pressure ulcers, excluding Stage 1. Inclusion of other stages, including “unstageable”, depends on the level of exudate and lack of infection.
- Non-ischemic diabetic foot ulcers (Wagner Grade 1 or 2)
- Leg ulcers

[figure not shown]
#### *Dressing description*

ALNB is a quadrilobed or rectangular shaped exudate management wound dressing which is a new variant of ALLEVYN LIFE. ALNB is a non-bordered dressing, allowing it to be cut to the shape of the wound before use. ALNB uses a low-tack silicone adhesive. ALNB incorporates an opaque, moisture-vapor permeable (MVP) top film that allows for some masking of the exudate penetration.

[figure not shown]
#### *Construction of ALNB*

ALNB is a composite dressing; it is made up of 4 layers (see Figure 6.1.1-1), including the MVP top film, a superabsorbent layer, a foam layer, and a wound contact layer (see Figure 6.1.1-2). The wound contact layer is perforated to allow the transfer of exudate from the wound into the dressing.

**Figure 6.1.1-1: ALLEVYN Life Non-Bordered Dressing Structure**

**Figure 6.1.1-2: Wound Contact Layer, Showing Regular Perforation**

The device is fitted with handles to protect the silicone wound contact layer prior to application and to facilitate application of the dressing to the wound. The handles are removed during the application process.

*Manufacturer and available sizes*

ALNB is manufactured by Smith & Nephew Medical Limited, [name].

ALNB is available in three sizes (see Table 6.1.1-1). Shapes and relative sizes are shown in Figure 6.1.1-3.

**Table 6.1.1-1: ALLEVYN Life Non-Bordered Dressings for Evaluation**

Product Code	Dressing Size and Packaging
66801748	10.5 x 10.5 cm Dressing; Carton of 10
66801749	16 x 16 cm Dressing; Carton of 10
66801751	10 x 20 cm Dressing; Carton of 10

**Figure 6.1.1-3: ALLEVYN LIFE Non-Bordered Dressings (Not Actual Size)**

*Number of investigational devices used on each subject*

ALNB is designed to be worn for up to seven days. Subjects randomized to ALNB will have their dressings changed according to individual clinical need (see Section 6.2). The total duration of treatment with ALNB will also depend on factors such as wound healing, topical wound treatments, or suitability of continued treatment with ALNB. If the wound does not heal, the maximum study treatment period will be twelve weeks. Thus, the number of ALNB dressings used by each subject will differ.

### 6.1.2 Comparator Products

Subjects allocated to the comparator arm of the study shall receive SC, defined as any protective wound dressing(s) which, in the opinion of the Investigator, would be beneficial in treating the wound, other than:

- variants of ALLEVYN
- topical antimicrobials, such as Acticoat™, Iododsorb™, silver products, etc.
- negative pressure wound therapy

Standard care should correspond as closely as possible to normal clinical practice, and dressings used routinely within each individual research site.

### 6.1.3 Ancillary Product

At Smith & Nephew's discretion, the following ancillary products may be made available to research sites for use on study subjects during this study – OPSITE™, PROFORE™, DURAFIBER™, and INTRASITE™. However, this study does not require any particular ancillary dressing to be used to secure ALNB. Rather, selection of ancillary dressings should be determined based on clinical requirements.

Per the IFU, physicians may use INTRASITE under ALNB, as clinically warranted.

## 6.2 PRODUCT USE

[figure not shown]
### 6.2.1 HCP Training

Study center personnel with responsibilities for the medical care of subjects and/or application of the investigational product (ALNB) will be trained on the use and application of ALNB prior to enrolling subjects into the study. HCP training will only occur following completion of the clinical trial agreement. HCP training will involve a presentation on the correct application and use of ALNB, including frequency of dressing change. ALNB is a moderate to highly absorbent dressing which can be worn for up to seven days and should be changed as directed in the product IFU (see Sections 6.2.3 and 21.1), rather than due to routine schedule or convenience.

## 6.2.2 Application

Application of the product will follow the directions from the product IFU (Figure 6.2.2-1).

**Figure 6.2.2-1: ALNB Application**

Study subjects will not be trained or expected to apply or change their own dressings. All dressing changes should occur at the Investigator site.

[figure not shown]
## 6.2.3 Dressing Change

HCP will be instructed to follow directions given in the product IFU (Figure 6.2.3-1) when changing ALNB.

### Figure 6.2.3-1: Instructions for changing ALNB

#### Frequency of change

During the early stages of treatment inspect the dressing frequently. Dressings can be left in place for up to 7 days. Dressings should be changed depending on the condition of the wound and surrounding skin or when exudate is within 0.5cm (3/16in) of the dressing edge. The diagram below is for guidance only and the decision of when to change should be dependent upon clinical assessment and local protocols:

**Removal:** Lift one corner and slowly peel back until completely removed.

### 6.2.4 Storage of ALNB

ALNB should be stored in a dry place, at less than 77°F (25°C), and away from sunlight.

### 6.2.5 Concomitant Dressings

With the exception of dressing/bandaging placed over ALNB for secondary retention or compression, the only other dressings that are permitted to come into contact with the wound bed and for use in conjunction with ALNB within the study are:

- Intrasite Gel for necrotic and sloughy wounds
- Durafiber for deeper wounds (Durafiber Ag should not be used due to its antimicrobial action).

### 6.3 PACKAGING AND LABELING

Packaging and labeling will be prepared to meet regulatory requirements.

### 6.3.1 Test Product

Smith & Nephew will supply each site with ALLEVYN LIFE Non-Bordered for use during the study. All test articles will be supplied in standard commercial packaging, clearly showing the batch number and expiry date. A label with the following information will be affixed to the ALNB packaging without obscuring any regulatory text:

- Smith & Nephew, Inc. Fort Worth, Texas
- Study Number
- Store at room temperature
- For Investigational Use Only

### 6.3.2 Comparator Article

SC, as defined in Section 6.1.2., will serve as the control treatment. Dressings used as SC will be those used routinely by the participating research site. Participating sites will acquire these routine dressings for use during the study.

Due to the variability in the product that will be used in the comparator group, S&N will not supply or label these dressings.

### 6.3.3 Ancillary Products

Any ancillary products supplied by Smith & Nephew will not be labeled.

## 6.4 PRODUCT ACCOUNTABILITY PROCEDURES

The Sponsor will keep a detailed record of all ALNB dressings supplied to each site. Confirmation of receipt by the Investigator will also be retained.

The receipt and dispensing of each dressing will be recorded on appropriate accountability forms available for verification by the Sponsor or its designated representative at each monitoring visit. Overall accountability for the accuracy of these records is the responsibility of the Investigator or designated individual maintaining the inventory, which shall include details of receipt, use,

waste, returns, and collection, etc., of product supplies. Used dressings will be appropriately destroyed per local requirements for clinical waste by the site staff without verification by the study monitor.

All cartons will be clearly identified per the labeling in Section 6.3. The Study Monitor will ensure that the procedures and records are in place for appropriate reconciliation of all test articles. As part of monitoring, the Study Monitor will check that the site personnel are following the procedures and completing all of the necessary documentation.

In addition, any ancillary products (PROFORE, INTRASITE, etc.) supplied to the site by the Sponsor will require appropriate accountability.

## **7. SUBJECTS**

### **7.1 SUBJECT POPULATION**

Approximately 40 adult subjects (18 years of age or older) with a moderate to highly exuding chronic ulcer that requires a dressing, but which does not, in the opinion of the Investigator, require topical antimicrobial treatment, will be recruited.

Chronic wounds will include LU (arterial/mixed etiology leg ulcers or venous leg ulcers requiring compression therapy), PU, and non-ischemic DFU. For subjects with multiple ulcers, the largest ulcer meeting the inclusion/exclusion criteria will be studied as the reference ulcer.

The following minimum numbers of wound types will be enrolled in each study group:

- ALNB: 5 DFU, 5 PU, 5 LU
- SC: 3 DFU, 3 PU, 3 LU.

### **7.2 INCLUSION CRITERIA**

1. The subject must provide informed consent to participate in the study; see Section 9.1.
2. The subject must be eighteen (18) years of age or older.
3. The subject must be willing and able to make all required study visits.

**CONFIDENTIAL DOCUMENT**

This document contains confidential information, which is the property of Smith & Nephew, Inc. Do not copy, disclose, or circulate without written authorization from the appropriate Smith & Nephew personnel

4. The subject must be able to follow instructions and be deemed capable of completing the CWIS questionnaire.
5. The subject must present with a chronic ( $\geq 4$  weeks duration) ulcer which meets all of the following criteria:
  - (a) The ulcer is classified as either:
    - a pressure ulcer
    - a non-ischemic diabetic foot ulcer
    - a leg ulcer (arterial/mixed etiology leg ulcers or venous leg ulcers requiring compression therapy)
  - (b) The ulcer is, in the opinion of the Investigator, moderate to highly exuding.
  - (c) The ulcer would, in the opinion of the Investigator, benefit from a protective dressing.
  - (d) The ulcer is not infected based on clinical signs/symptoms.
6. A subject with a DFU must have an ankle-brachial index (ABI) of 0.7 or greater, as measured within 30 days of the Screening Visit.

Subjects with a VLU that will use compression therapy should have an ABI that meets the requirements of the IFU for the selected compression device.

### 7.3 EXCLUSION CRITERIA

1. Contraindications or hypersensitivity to the use of the ALLEVYN LIFE Non-Bordered, comparator, ancillary products, or their components.
2. Participation in the treatment period of another clinical trial within 30 days of Visit 1 or planned participation overlapping with this study.
3. The subject's reference ulcer is being treated with a topical antimicrobial dressing.

4. Subjects with skin features (e.g. tattoos, skin color, pre-existing scarring) which, in the opinion of the Investigator, could interfere with the study assessments.

5. Subjects who have participated previously in this clinical trial.

6. Subjects with a history of poor compliance with medical treatment.

7. Subjects with a medical or physical condition that, in the opinion of the Investigator, would preclude safe subject participation in the study.

#### **7.4 SCREENING LOG**

Participating study sites are required to document all screened subjects initially considered for inclusion in this study (i.e. a subject who gives informed consent). If a subject is excluded from the study, the reasons for exclusion will be documented in the subject's source documents and noted on the Screening Log.

#### **7.5 ENROLLMENT**

The point of enrollment in the study is when the subject has signed and dated the informed consent document and met all the eligibility criteria.

The anticipated enrollment period is approximately nine (9) months.

#### **7.6 WITHDRAWAL**

Subjects may be withdrawn early from study treatment for the following reasons:

- Closure of the reference ulcer.
- If the subject misses two (2) consecutive dressing changes/study visits, interrupting treatment for longer than seven (7) days.
- At the discretion of the Investigator due to:
  - A change in treatment that is clinically warranted
  - An adverse event (AE)

- Any other significant reason identified by the Investigator

Subjects may be withdrawn entirely from the study for the following reasons:

- At their own request (i.e. withdrawal of consent).
- Failure to complete the CWIS appropriately at Visit 1.
- At the discretion of the Investigator due to:
  - Concurrent illness
  - Adverse device effects (ADE)
  - Non-compliance (e.g. did not follow instructions).
  - Lost to follow-up (LTFU)
  - Any other significant reason identified by the Investigator

Where subjects withdraw consent, the Investigator should make a reasonable effort to ascertain the reason(s), while fully respecting the subject's privacy.

Subjects withdrawn from the study because the CWIS is not complete will be replaced by enrolling a new study subject.

[figure not shown]

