#### **9.2.4 Visit 2 (Day 21 ± 3 days) and Visit 3 (Day 42 ± 4 days)**

Visits 2 and 3 will consist of an on-site visit. These visits should coincide with the normal timing of dressing changes, i.e. seven (7) days or fewer for ALNB.

Subjects who have already had their treatment discontinued/been withdrawn from treatment and no longer require a dressing change shall be followed up either by an on-site visit or by telephone. In such cases, the main purpose will be to collect CWIS outcome data and any data related to AE (if applicable).

- 1. Question subjects regarding any changes in health or concomitant treatment.
- 2. All subjects must complete the CWIS, including those withdrawn from treatment unless they have been withdrawn from the study.

Give the subject a printed copy of the CWIS and allow sufficient time to complete it. Assist with completion if asked. For any subject followed up by telephone, read the complete CWIS and record the subject's responses accurately. Ensure that the subject has completed the CWIS appropriately. A single valid response should be recorded for each item.

NOTE: subjects who cannot read/write may have the CWIS read aloud to them and the subject's responses recorded. Ensure this process is noted in the source documents.

3. Ask the subject to assess the comfort of wearing the dressing since the last visit (see Section 9.5.8).
4. Assess the movement of the dressing (see Section 9.5.9).
5. Remove the old dressing and inspect the ulcer. Complete an ulcer assessment (see Section 9.5.1).

*Notes: 1) A full ulcer assessment is not necessary if the subject has already been discharged or withdrawn from treatment.*

*2) Not applicable if this visit is completed via a phone call.*

6. Assess the level of pain experienced by the subject when the dressing is removed (see Section 9.5.6).
7. Assess the ease of dressing removal, leakage, and absorption under compression (see section 9.5.10)
8. Take a photograph of the ulcer, showing the ruler as supplied. Record any debridement and the method of debridement, and take a photograph of the ulcer immediately prior to and following debridement.

Photograph the used dressing on both sides, together with any secondary dressing.

Note: Photographs are not necessary if the subject was discharged or withdrawn from treatment at a previous visit.

9. Redress the ulcer, if clinically indicated, using an appropriate dressing according to group allocation:

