### 9.2.6 Treatment Discontinuation

A subject may be withdrawn from treatment early and discharged from care (see Sections 7.6 and 9.3) prior to follow-up at Visit 2, Visit 3, or the End of Study Visit. However, these subjects will still be retained as active study participants, even though their study treatment has ended. When this occurs, the subject will continue as an active participant for the remainder of the twelve (12) week study period, completing all remaining study visits (either by attending site appointments or by telephone if necessary), to gather complete CWIS data.

1. Question subjects regarding any changes in health or concomitant treatment.
2. Give subject given a copy of the CWIS and allow sufficient time for them to complete it. Assist with completion if asked. For any subject followed up by telephone (see above), read the complete CWIS and record the subject's responses accurately. Ensure that the subject has completed the CWIS appropriately. A single valid response should

be recorded for each item of the CWIS.

NOTE: subjects who cannot read/write may have the CWIS read aloud to them and the subject's responses recorded. Ensure this process is noted in the source documents.

3. Ask the subject to assess the comfort of wearing the dressing since the last visit (see Section 9.5.8).
4. Assess the movement of the dressing. (see Section 9.5.9).
5. Remove the old dressing and inspect the ulcer. Complete an ulcer assessment (see Section 9.5.1).

*Notes: 1) A full ulcer assessment is not necessary if the subject has already been discharged or withdrawn from treatment.*

*2) Not applicable if this visit is completed via a phone call.*

6. Assess the level of pain experienced by the subject when the dressing is removed. (see Section 9.5.6).
7. Assess the ease of dressing removal, leakage, and absorption under compression (see section 9.5.10).
8. Take a photograph of the ulcer, showing the ruler as supplied. Record any debridement and method of debridement, and take a photograph of the ulcer immediately prior to and after debridement.

Photograph the used dressing on both sides, together with any secondary dressing.

9. If any AE or DevD are observed or reported, they must be recorded as instructed in Section 12 (Adverse Events and Device Deficiencies).

Photograph the dressing only if reporting a device deficiency.

10. Redress the ulcer, if clinically indicated, using an appropriate dressing.  

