### **12.1.1 Adverse Event**

An Adverse Event (AE) is any untoward medical occurrence temporally associated with the use of an investigational medicinal product or device, whether or not considered causally related to that product/device. An AE can be any unfavorable and unintended sign (for example, an abnormal laboratory finding), symptom, or disease.

AE is used both to refer to AE which are not serious or device related and as an umbrella term referring to adverse events of all classifications.

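### Protocol 7.6 does not settle whether a device-related event ends treatment only or study participation, so week-6 CWIS-PSDL scores can be lost for reasons linked to the dressing

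*Protocol*

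**What the plan says.** Protocol 7.6 separates two kinds of withdrawal.

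- **From treatment.** The list opens "Subjects may be withdrawn early from study treatment for the following reasons". It includes closure of the ulcer, repeated missed visits and, at the Investigator's discretion, an adverse event.
- **From the study.** The list opens "Subjects may be withdrawn entirely from the study for the following reasons". At the Investigator's discretion it includes "Concurrent illness", "Adverse device effects (ADE" and "Non-compliance (e.g. did not follow instructions".

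The kind of withdrawal decides what is collected afterwards. For treatment-only withdrawals, 9.2.6 says that "these subjects will still be retained as active study participants, even though their study treatment has ended", with the remaining visits completed on site or by telephone so that CWIS data are complete. For Visits 2 and 3, 9.2.4 says: "All subjects must complete the CWIS, including those withdrawn from treatment unless they have been withdrawn from the study". Section 9.2.5 repeats this for week 12.

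Section 9.3 confirms that safety reasons, device effects and non-compliance can end participation. For early leavers it asks for the End of Study Visit where possible.

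Protocol 12.1.2 defines an adverse device effect as an adverse event judged related to the investigational or comparator device. Section 12.1.1 uses the abbreviation AE in two senses: a narrow one (neither serious nor device-related) and "as an umbrella term referring to adverse events of all classifications".

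**The concern.** The primary endpoint is the change in CWIS-PSDL from baseline to week 6. The scale asks about wound pain, leakage, odour and discomfort from the dressing. A subject who stops because of a reaction to the dressing may well score differently on these items from a subject who continues. If that reaction can also take the subject out of outcome collection, the missing week-6 scores depend on the experience that the scale is meant to measure.

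Treatment is not blinded (8.3), and the decision rests with an Investigator who knows the allocation. The primary objective is estimation, and 8.2 intends the result to support product claims and to supply an effect size for a later trial. A systematic error in the estimate therefore matters more here than a loss of power.

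**Working it through.** **Step 1: which list governs a device effect?** Section 7.6 does not say in which sense it uses AE.

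- In the umbrella sense, a device effect is on both lists, with opposite consequences for the CWIS, and no rule chooses between them.
- In the narrow sense, the lists do not overlap, but the device-related event is then the one that leads out of the study.

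On either reading, a device effect is a listed ground for ending the duty to collect the CWIS. Non-compliance is unclear too: missed visits that interrupt treatment are on the treatment list, while failure to follow instructions is on the study list.

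**Step 2: does 9.3 close the gap?** Only in part. The visit is requested where possible, 9.2.5 places it at Day 84 ± 4, and 9.3 gives no other timing for early leavers. It yields at most one CWIS, which need not fall at week 6. SAP 7.4 flags out-of-window visits but does not say how their scores are used.

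**Step 3: does the SAP repair the loss?**

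- Exit after the week-3 CWIS: the week-3 score is carried to week 6 (SAP 7.3).
- Exit before any post-baseline CWIS: the score stays missing (SAP 7.3).
- No post-baseline assessment at all: the subject is outside the FAS (SAP 7.2).
- Sensitivity analysis: the same ANCOVA without imputation (SAP 7.9), which drops these subjects.
- Per-protocol analysis: early withdrawals other than for closure are excluded (SAP 7.2).

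None of these uses an outcome observed after the exit.

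**Step 4: size.** The documents give no device-effect rate, SD or expected effect. The only figure to reproduce is the allocation: 25 × 8/5 = 40, of which 40 × 3/8 = 15 are SC. It reproduces.

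Assume that k of 25 ALNB subjects are lost and none on SC. Let d be the amount by which the lost subjects' true week-6 result is worse than the value carried forward or, if they are dropped, than that of retained subjects. The ALNB mean is then overstated by k/25 × d:

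| k | d = 10 | d = 15 | d = 20 |
|---|---|---|---|
| 1 | 0.4 | 0.6 | 0.8 |
| 2 | 0.8 | 1.2 | 1.6 |
| 4 | 1.6 | 2.4 | 3.2 |

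With losses in both arms and the same d, the bias in the difference is (k_ALNB/25 − k_SC/15) × d. At d = 10:

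- 2 ALNB and 1 SC lost: (0.080 − 0.067) × 10 = 0.13 points.
- 5 ALNB and 3 SC lost: (0.20 − 0.20) × 10 = 0.
- 0 ALNB and 1 SC lost: −0.67 points, so the sign reverses.

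**Step 5: precision.** The SE of the difference is proportional to √(1/25 + 1/15) = 0.3266. With 2 ALNB subjects lost it is √(1/23 + 1/15) = 0.3319, an increase of 1.6%; with 5 lost it is 0.3416, an increase of 4.6%. The issue is selective loss, not power.

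**The case against.** The strongest reply is that nothing here is compulsory. Both lists are permissive, an Investigator may handle a device effect as treatment withdrawal with CWIS continuing, and 9.3 says that treatment-only withdrawals do not automatically leave the study. Protocol 4.2.2 describes reactions to the parent dressing as infrequent, generally local and mild, so few subjects may be affected. With an assumed SD of 15 to 20 points, the SE of the difference at 25:15 is about 4.9 to 6.5 points. A shift of 1.2 points is then about a fifth to a quarter of one SE, in a pilot sized on feasibility. All of this stands, and it limits the weight of the point. It does not say which list applies.

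A reader might also infer more than the documents support:

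- **That other adverse events end treatment only.** Concurrent illness, any other significant reason (7.6) or risk to the subject (9.3) can also end participation.
- **That a device effect stops all CWIS collection.** Section 9.3 still requests one visit that includes the CWIS.
- **That non-compliance is device-related.** The documents do not say so.
- **That the bias must favour the arm with more device effects.** A week-3 score taken during a reaction may be poor, and the subject may recover afterwards on SC. LOCF would then understate week 6. Device effects can also occur with the comparator.
- **That the FAS fails intention to treat for this reason.** A subject who has attended one post-baseline assessment stays in the FAS after withdrawal, and visits are at least weekly (8.1).

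**Conclusion.** The point holds as a gap in follow-up rules. Sections 7.6 and 9.3 allow week-6 CWIS-PSDL scores to be lost, at the discretion of an unblinded Investigator, for reasons linked to the assigned dressing in either arm, and the planned analyses do not correct informative loss. SAP 7.6 will tabulate withdrawal reasons by arm, which shows whether losses differ but does not restore the scores.

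The direction and size of any bias are unknown. The range of 0.4 to 3.2 points rests on three assumptions that the documents do not supply: 1 to 4 ALNB subjects lost, none lost on SC, and a deficit of 10 to 20 points. The bias is zero if proportions lost and gaps are equal in the two arms. The documents do not support a claim that the trial is biased towards ALNB. The change is worth making because it is cheap and the procedure already exists.

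**What to change.** Reconcile Protocol 7.6, 9.2.4, 9.2.5, 9.2.6 and 9.3 on CWIS follow-up. State that stopping the study dressing for an adverse device effect or for non-compliance does not by itself end CWIS collection. While consent continues and the subject can be contacted, collect the CWIS at the remaining visits, on site or by telephone, under the existing 9.2.6 procedure.

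Leave unchanged the rule that replaces subjects with an incomplete CWIS at Visit 1, and all clinical decisions on treatment. The change concerns data collection only.

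The cost is a short protocol amendment with IRB approval, which Protocol 15 reserves for exceptional cases once the study has started, and a few telephone contacts.
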